4.3 ProSpA-CD-Assess phase

4.3.1 Assessment of patients with lesions on MRE consistent with axSpA (cases)

Patients with lesions on MRE consistent with axSpA (and no known diagnosis of SpA) will be informed by telephone and letter by the gastroenterology team and referred to [name] NHS rheumatology SpA clinic. They will also be sent separately an invitation letter, participant information sheet (PIS) and reply slip (study interest form with a stamped-addressed envelope for returns) for the ProSpA-CD-Assess phase of the study by the gastroenterology team. CD subjects with a known diagnosis of SpA who are already under review by rheumatology and who have lesions on MRE consistent with axSpA will also be considered as cases and will be sent an invitation letter, PIS and study interest form. However, they will instead be invited to attend the rheumatology SpA research clinic to be assessed for axSpA (with the control group) as this will be considered to be outside of their routine NHS care.

In the NHS SpA clinic, the patients will be assessed by a single rheumatologist ([name], in a supernumerary capacity with salary funded by the research grant) for clinical evidence of axSpA *as per* standard of care using the 2009 ASAS criteria for axSpA, modified New York criteria for AS and CASPAR criteria for PsA (see Appendices 5, 6 & 7). The assessment will include a clinical history, examination (including BASMI, 68 tender joint count, 66 swollen joint count, the SPARCC enthesitis index and for skin or nail psoriasis), PROMs (BASDAI, BASFI, VASbp, ASDAS and HAQ-DI), blood samples (FBC, renal function, LFTs, CRP and ESR unless performed in the preceding month, and HLA-B27 unless previously performed) and stool samples (the monitoring of IBD luminal activity with faecal calprotectin is well established [41, 42]; stool samples will therefore also be collected to measure faecal calprotectin concentrations unless performed in the preceding month). During the consultation, the ProSpA-CD-Assess phase of the study will also be discussed further and patients will be provided with the opportunity to ask any questions they may have regarding the study. If they agree to participate in the study and meet the inclusion criteria, then written informed consent will be taken. The blood and stool tests will be performed as per standard of care if clinically indicated or for research and funded by the research grant if not clinically indicated.

If considered to be clinically indicated as per the above assessments, a dedicated axial MRI scan of the spine and sacroiliac joints will be requested (NHS funded) *as per* standard of care. If considered not to be clinically indicated as per these assessments, consenting subjects will undertake a dedicated axial MRI scan of the spine and sacroiliac joints for research (research grant funded).

As part of the ProSpA-CD-Assess phase of the study, all participants will be asked and consented to have blood (20mls) and stool samples taken for research. These will be stored and undergo analysis at a later date for biomarkers (serum, genotyping, proteomics, microbiome) of axial SpA occurrence and phenotype. Requests for research grants to fund these analyses are currently in progress.

The NHS SpA clinic encounter will be summarised by letter to the patient and copies will also be sent to the patients GP and gastroenterology consultant. The cases (excluding CD subjects with known

SpA who are MRE+ and already under rheumatology review) will then be followed up for their second review in the NHS rheumatology SpA clinic approximately 6 months later and will complete the following PROMs; BASDAI, BASFI, VASbp, ASDAS & HAQ-DI. Each patient will also be examined using the BASMI, 68 tender joint count, 66 swollen joint count, the SPARCC enthesitis index, and for skin or nail psoriasis. The following investigations will also be performed as per standard of care if not performed within the preceding month; FBC, renal function, LFTs, CRP and ESR. The patients will also be reviewed in the SpA clinic at an earlier date if indicated for treatment or clinical reasons.

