1.2 Aim

The aim of this study is to determine the sensitivity and specificity of magnetic resonance enterography (MRE) as a screening tool for axial spondyloarthritis (axSpA) in a cohort of adult patients with Crohn's disease (CD) in a secondary-care hospital, using dedicated axial magnetic resonance imaging (MRI) with clinical assessment as the gold standard.

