4.3.2 Assessment of subjects with no lesions on MRE consistent with axSpA (controls)

Subjects (including those with a known diagnosis of SpA) who have consented to having their MRE scans reviewed, but who do not have lesions consistent with axSpA, will be informed in writing of this by the gastroenterology team. They will also be advised that they may be invited to enter the study as a control subject if they are randomly selected through matching (age and sex) to the enrolled 'MRE+ cases' (1:1 ratio). Matched potential control subjects will then be sent an invitation letter, PIS and reply slip (study interest form with a stamped-addressed envelope for returns) by the gastroenterology team to attend the rheumatology SpA research clinic to be assessed by [name] for clinical evidence of axSpA. CD subjects with a known diagnosis of SpA who are already under review by rheumatology and who have lesions on MRE consistent with axSpA will also be invited to attend this clinic for review outside of their routine NHS care but will be considered as cases. Informed consent for study participation in the SpA research clinic will be performed at the start of the consultation. The same clinical assessments, blood and stool samples and dedicated axial MRI scan of the spine and sacroiliac joints will be performed in this control group and in the group of CD subjects with a known diagnosis of SpA who are MRE+ as in the other cases, but will be funded by the research grant unless clinically indicated.

Control subjects in whom there is no evidence of axSpA (by ASAS, modified New York or CASPAR classification criteria) will be informed by letter, which will also be copied to the subjects GP and gastroenterology consultant. Control subjects who do have evidence of axSpA will be informed by letter (also copied to GP and gastroenterology consultant) and asked to return to [name] NHS rheumatology SpA clinic for ongoing care. CD subjects who already have a diagnosis of SpA (both in the control group and cases group) and are already under review by a rheumatology team will be informed by letter of the research clinic outcome and will be followed up as planned by their primary rheumatology team. We will also send a copy of the clinic letter to their GP, gastroenterology consultant and named rheumatology consultant to inform them of the clinic findings and to notify them of any outstanding tests/ management plans that may need to be considered at the next clinic review.

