5.2.2.1 Consent for retrospective review of the MRE scans (ProSpA-CD-Screen phase)

The gastroenterology team will write to all patients with CD and MRE scans since 2015 to ask for consent to review the images for evidence of axSpA. This correspondence will include a PIS and consent form with a stamped-addressed envelope for returns. The pack will also contain a BASDAI questionnaire with six simple questions relating to symptoms of axial inflammatory pain. These six questions, answered on a 1-10 VAS will pose low burden on the subject and be optional to complete, but will markedly help the research team gauge the impact of selection bias on the study given that there may be a preponderance of patients with axial pain willing to participate in the study.

5.2.2.2 Consent to enter the study as a case or control subject (ProSpA-CD-Assess phase)

Patients with lesions on MRE consistent with axSpA (and no known diagnosis of SpA) will be informed of this by the gastroenterology team (by telephone and letter) and be referred to [name] NHS SpA clinic for further clinical assessment. Once informed, they will also be invited by post to enter the research element of the study, with an invitation letter, accompanying PIS and reply slip (study interest form) with a stamped-addressed envelope to permit the patient to express if they do or do not wish to participate in the study.

CD subjects with a known diagnosis of SpA who are already under the care of a rheumatology team and have lesions on MRE consistent with axSpA will also be contacted by telephone and letter by the gastroenterology team. The subjects will then be sent a separate invitation letter, PIS and reply slip (study interest form) with a stamped-addressed envelope to permit the subject to express if they do or do not wish to participate further.

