6.7 Definition of the end of study

This will be the date of the last visit of the last participant

If a subject is unable to undertake these assessments immediately, a convenient future research clinic appointment will be made for them and associated travelling costs will be reimbursed.

This study schedule will pose low burden and inconvenience to the subject. Blood sampling will take place at the time of clinical measurements, and are of low total volume (40ml). The subjects will be asked to return to have the dedicated axial MRI scan and to minimise inconvenience, they will be encouraged to return their stool samples when they attend for the scan. Control subjects will be reimbursed for travel and parking costs, and the case subjects will also be reimbursed for any extra travel or parking costs incurred through participating in the study.

Clinical questionnaires are those that would be completed *as per* standard in usual clinical care (except for the control group). However, as we are asking questions in some of the PROMs about the subject's experience of illness, this may cause a degree of upset. Therefore to minimise distress, the clinician ([name]) will talk the subject through each questionnaire prior to completion at the initial clinic visit. In addition, our participation information sheets will stress that participation is voluntary and that the subject can withdraw from the study at any time without their care being affected. Our participation information sheets will also explain the processes taken to maintain anonymity and confidentiality.

The correspondence (invitation letters and PIS) for CD subjects with and without known SpA will have different content to reflect this and to reduce any potential concern or anxiety.

The MRI scan is a non-invasive procedure and the subjects will already have had the experience of having a MRI scan (MRE). However, some subjects may find it difficult to have the MRI scan if they suffer from claustrophobia. Therefore, the MRI scan procedure will be explained to the subject during the initial consultation and they will be provided with the opportunity to ask any questions. We will also emphasise that this is voluntary and that they have the right to decline this or any other part of the study.

7. Data collection, source data and confidentiality

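### The clinical part of the gold standard is not blinded to the MRE result, which can be expected to raise apparent accuracy against the MRI-plus-clinical composite

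*Combined protocol and SAP*

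**What the plan says.** Section 1.2, repeated in 3.1, defines the reference as a composite: "using dedicated axial magnetic resonance imaging (MRI) with clinical assessment as the gold standard".

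Under 4.3.1, patients with lesions and no known SpA "will be informed by telephone and letter by the gastroenterology team and referred to" the NHS SpA clinic. The assessor there applies the ASAS, modified New York and CASPAR criteria: "In the NHS SpA clinic, the patients will be assessed by a single rheumatologist". Under 4.3.2, subjects without lesions are told so in writing. Those drawn as matched controls are then invited "to attend the rheumatology SpA research clinic to be assessed by [name] for clinical evidence of axSpA". MRE-positive patients with known SpA are contacted by telephone and letter (5.2.1.2, 5.2.2.2) and seen in the research clinic alongside the controls (4.3.1).

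Before PROMs are completed, the clinician "will talk the subject through each questionnaire prior to completion at the initial clinic visit" (text under 6.7). One symptom measure comes earlier. The Screen-phase consent mailing is described in 5.2.2.1: "The pack will also contain a BASDAI questionnaire with six simple questions relating to symptoms of axial inflammatory pain". It is optional, and its stated purpose is to gauge selection bias.

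Section 4.2.1 blinds the MRE readers to co-morbidities other than CD and anonymises the images given to the tie-break reader. No section masks the clinical assessor or the patients to the MRE result, and none provides a second clinical assessor or adjudication.

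**The concern.** In an accuracy study the reference should be established without knowledge of the index test. Here the history, the examination and the PROMs all come after disclosure of the MRE result, to an assessor who for most subjects can read that result from the clinic list.

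Several exposed items bear on classification. ASAS applies only to patients with chronic back pain that began before age 45 (Appendix 5). The modified New York clinical criteria include inflammatory back pain with stiffness and restricted lumbar motion (Appendix 6). A borderline history is more likely to be read as axSpA in someone known to have lesions, and less likely in someone known to have none.

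Three results are at stake: sensitivity, specificity and AUC against the composite; the proportion of MRE-positive patients meeting criteria (objective 2); and the tests of MRE score against PROMs in 8.2. A larger sample would not remove the bias.

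**Working it through.** **Who knows what before assessment**

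| Group | Contact before the visit | Clinic | Does the clinic reveal MRE status? |
|---|---|---|---|
| MRE+, no known SpA | Told by telephone and letter (4.3.1, 5.2.2.2) | NHS SpA | Yes, positive |
| MRE−, no known SpA, control | Told in writing (4.3.2, 5.2.2.2) | Research | Yes, negative |
| MRE+, known SpA | Contacted by telephone and letter (5.2.1.2, 5.2.2.2) | Research | Not by itself |
| MRE−, known SpA, control | Told in writing (4.3.2, 5.2.2.2) | Research | Not by itself |

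For patients without known SpA, clinic and MRE status therefore coincide.

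**Direction**

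Let a share u of MRE+/reference-negative patients (FP) be called reference-positive, and a share d of MRE−/reference-positive patients (FN) be called reference-negative. Then

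- sensitivity = (TP + u·FP) / (TP + u·FP + (1 − d)·FN)
- specificity = (TN + d·FN) / (TN + d·FN + (1 − u)·FP)

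Both rise with u and with d, whatever the starting table.

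**Size, for illustration only**

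The plan gives no figure for this bias. From 8.1 come an MRE-positive rate of 15% (the lower of its two sources), a sensitivity of 60%, and at least 66 cases and 66 controls. The 66 reproduces: 445 × 0.15 = 66.75. (The 445 does not follow from 990 × 0.5 = 495, but nothing below uses it.) The positive predictive value (PPV: 0.50, 0.65, 0.80) and u = d = 10% are assumptions.

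*Reweighted to all screened subjects.* As proportions of those screened: TP = 0.15 × PPV, FP = 0.15 − TP, FN = TP × 0.4/0.6, TN = 0.85 − FN.

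| PPV | TP | FP | FN | TN | Sensitivity | Specificity |
|---|---|---|---|---|---|---|
| 0.50 | 0.0750 | 0.0750 | 0.0500 | 0.8000 | 0.600 → 0.647 | 0.914 → 0.923 |
| 0.65 | 0.0975 | 0.0525 | 0.0650 | 0.7850 | 0.600 → 0.637 | 0.937 → 0.944 |
| 0.80 | 0.1200 | 0.0300 | 0.0800 | 0.7700 | 0.600 → 0.631 | 0.963 → 0.966 |

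First row: (0.0750 + 0.0075) / (0.0825 + 0.0450) = 0.0825/0.1275 = 0.647. With u = d = 5%, sensitivity is 0.615 to 0.624; with 20%, 0.663 to 0.692.

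*Unweighted 66 + 66.* TP = 66 × PPV, FP = 66 − TP, FN = 66 × (FN share above)/0.85, TN = 66 − FN.

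| PPV | FN among 66 controls | Sensitivity | Specificity |
|---|---|---|---|
| 0.50 | 3.9 | 0.895 → 0.912 | 0.653 → 0.678 |
| 0.65 | 5.0 | 0.895 → 0.909 | 0.725 → 0.747 |
| 0.80 | 6.2 | 0.895 → 0.906 | 0.819 → 0.836 |

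*Objective 2.* If meeting criteria is taken as reference-positive, the proportion becomes PPV + 0.10 × (1 − PPV): 0.50 → 0.55, 0.65 → 0.685, 0.80 → 0.82.

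**The case against.** Five points on the other side have force.

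- **Imaging and laboratory items count too.** Modified New York requires a radiological criterion, and CASPAR draws on psoriasis, nails, rheumatoid factor, dactylitis and radiographs. HLA-B27 and CRP are objective. Apart from its entry condition, the ASAS scheme does not appear in the text available here, so the weight of history within it cannot be shown. This stands: a reader might infer that self-report and judgement alone settle reference status, and the documents do not support that.
- **MRE is also compared with axial MRI.** Section 4.3.3 compares MRE and axial MRI scores, with the MRI read by two independent radiologists, and 8.1 bases the sample size on sensitivity against dedicated MRI. This stands as mitigation, and that comparison is less exposed. No masking of those radiologists to MRE status is stated, however, and the aim names the composite.
- **Disclosure is partly unavoidable.** Patients with lesions are being referred into NHS care and have to be told. This stands, and it is why the fix leaves disclosure alone.
- **The clinic does not always give the result away.** The research clinic mixes MRE-positive and MRE-negative patients with known SpA. This stands, though these patients too are contacted beforehand.
- **The questionnaire walk-through is there to reduce distress.** Nothing suggests that answers are steered. It matters only because it follows disclosure.

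**Conclusion.** The concern holds and should be fixed, but it does not invalidate the design. The clinical part of the composite is unblinded to the index test. Upward bias is the expected direction, not an observed one. Size depends on a PPV and a share of altered classifications that the documents do not give. At an assumed 10%, the reweighted table shows a gain of about 3 to 5 points in sensitivity and 0.4 to 0.8 in specificity. The unweighted 66 + 66 table shows 1 to 2 points in sensitivity and 1.7 to 2.5 in specificity.

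Two stronger readings go beyond the documents.

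- **A large, known inflation.** With an assumed PPV of 70%, 8% false negatives among 379 MRE-negative subjects and half of all discordant patients reclassified, sensitivity goes from 46.2/76.5 = 60% to 56.1/71.3 = 79%. None of those rates has a source in the plan. The example treats clinical judgement as if it alone fixed the reference, and it relies on a reweighting to all screened subjects that the plan does not describe. On the same PPV and false-negative assumptions, the unweighted 66 + 66 table with 10% reclassified moves sensitivity only from 46.2/51.48 = 89.7% to 48.18/52.93 = 91.0%.
- **One person in every role.** The repeated wording about a supernumerary assessor (1.5, 4.1) suggests the same rheumatologist in both clinics, and one MRE scorer is a rheumatology registrar. Names are removed, so neither identity can be checked. The point does not depend on them.

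**What to change.** 1. **Section 8.2.** Report sensitivity, specificity and AUC against the axial-MRI consensus alone, beside the MRI-plus-clinical composite. State in advance that any excess accuracy against the composite will be read as possible review bias. It is not proof, because the two references also measure different things.
2. **Section 5.2.2.1.** Add chronic back pain (yes/no), age at onset and the inflammatory back-pain items to the Screen-phase pack beside the BASDAI, so that they are recorded before the MRE is reviewed or its result disclosed. Keep the rheumatologist's history as the main clinical source, since postal self-report could weaken the reference. Repeat the criteria-based reference with the pre-disclosure answers as a sensitivity analysis.
3. **Section 8.2.** Test MRE score against the Screen-pack BASDAI as well as the clinic BASDAI. Report how many pack questionnaires are missing, because completion is optional.

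The cost is a short amendment, a slightly longer pack with possibly a slightly lower return, some missing data and a little extra analysis. No visit, test or member of staff is added, and the NHS referral route is unchanged. These steps do not blind the assessor; they show how far the results depend on post-disclosure information. Item 2 has to be in place before the packs go out, because pre-disclosure answers cannot be recovered once results have been sent.

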4.3.2 Assessment of subjects with no lesions on MRE consistent with axSpA (controls)

Subjects (including those with a known diagnosis of SpA) who have consented to having their MRE scans reviewed, but who do not have lesions consistent with axSpA, will be informed in writing of this by the gastroenterology team. They will also be advised that they may be invited to enter the study as a control subject if they are randomly selected through matching (age and sex) to the enrolled 'MRE+ cases' (1:1 ratio). Matched potential control subjects will then be sent an invitation letter, PIS and reply slip (study interest form with a stamped-addressed envelope for returns) by the gastroenterology team to attend the rheumatology SpA research clinic to be assessed by [name] for clinical evidence of axSpA. CD subjects with a known diagnosis of SpA who are already under review by rheumatology and who have lesions on MRE consistent with axSpA will also be invited to attend this clinic for review outside of their routine NHS care but will be considered as cases. Informed consent for study participation in the SpA research clinic will be performed at the start of the consultation. The same clinical assessments, blood and stool samples and dedicated axial MRI scan of the spine and sacroiliac joints will be performed in this control group and in the group of CD subjects with a known diagnosis of SpA who are MRE+ as in the other cases, but will be funded by the research grant unless clinically indicated.

Control subjects in whom there is no evidence of axSpA (by ASAS, modified New York or CASPAR classification criteria) will be informed by letter, which will also be copied to the subjects GP and gastroenterology consultant. Control subjects who do have evidence of axSpA will be informed by letter (also copied to GP and gastroenterology consultant) and asked to return to [name] NHS rheumatology SpA clinic for ongoing care. CD subjects who already have a diagnosis of SpA (both in the control group and cases group) and are already under review by a rheumatology team will be informed by letter of the research clinic outcome and will be followed up as planned by their primary rheumatology team. We will also send a copy of the clinic letter to their GP, gastroenterology consultant and named rheumatology consultant to inform them of the clinic findings and to notify them of any outstanding tests/ management plans that may need to be considered at the next clinic review.

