Subjects (including those with a known diagnosis of SpA) without evidence of axSpA on MRE will be contacted by the gastroenterology team (by letter) to inform them of the results and will also be advised that they may be invited to enter the study as a control subject. Once the cases have been identified and enrolled, control subjects will then be randomly selected (age and sex-matched in a case : control ratio of 1:1) to enter the research element of the study. The gastroenterology team will then write to these subjects to invite them to enter the study, accompanied by a PIS and a reply slip (study interest form) with a stamped-addressed envelope to permit the subject to express if they do or do not wish to participate further. Any CD subjects with a history of SpA who have been selected as a potential control subject will be sent a separate invitation letter, PIS and reply slip (study interest form) by the gastroenterology team.

During the clinic consultation for both cases and controls, the research study will be discussed further and the subject will be provided with the opportunity to ask any questions they may have regarding the study. If the subject subsequently agrees to take part in the study, then inclusion and exclusion criteria will be assessed and informed written consent will be taken.

6. Study schedule

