8.1 Power analysis

This study will aim to include all CD cases with MRE imaging since 2015; the estimated sample size is therefore 1100 cases.

To our knowledge, there are no studies comparing the sensitivity and / or specificity of MRE scans with gold standard dedicated MRI for the detection of sacroiliitis. However, there have been some studies comparing CT imaging with MRI and these found MRI to be up to 17% more sensitive for the detection of sacroiliitis than CT [48, 49].

Although MRE is expected to be more sensitive at detecting evidence of sacroiliitis than CT, our power calculation is based on the conservative estimate that MRE will detect at $\geq 60\%$ (sensitivity) of

the cases of sacroiliitis, when compared with the gold standard dedicated axial MRI scan. Therefore with 80% power and a two-tailed alpha of 0.05, it is estimated that ≥ 60 control subjects (MRE normal) will be required for the study. It is estimated that a sample of >60 cases (with abnormal MRE scans) would be needed since the sample size required to assess specificity for a screening test is less than that of sensitivity. Case and controls will be recruited in a ratio of 1:1. From the 1100 MRE scans already performed, it is expected that $\geq 90\%$ will have a diagnosis of CD, i.e. 990 subjects. We estimate that $\geq 50\%$ of postally invited participants will consent to participate in the study, giving approximately 445 MRE scans for review.

The two previous studies assessing IBD patients for evidence of sacroiliitis using MRE imaging estimated the prevalence to be 16.7% and 15% [27, 28]. We therefore estimate to recruit ≥ 66 subjects with positive MRE scans (cases) and ≥ 66 matched controls. This is a conservative estimate, greater than the minimum number needed to recruit.

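### The number of controls follows the number of cases that enrol, so losing more than 6 of the 66 forecast cases takes the MRE-negative group below section 8.1's minimum of 60, although about 378 MRE-negative subjects are available

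*Combined protocol and SAP*

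**What the plan says.** Three parts of the protocol fix the control rule. Section 4.3.2 has controls "randomly selected through matching (age and sex) to the enrolled 'MRE+ cases' (1:1 ratio"), and section 5.2.1.2 repeats this. Section 5.2.2.2 adds the order of events: "Once the cases have been identified and enrolled, control subjects will then be randomly selected". Sections 1.5 and 4.1 give the same ratio.

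Section 8.1 sets minimum numbers. Starting from an assumed sensitivity of at least 60%, 80% power and a two-sided alpha of 0.05, it says that "it is estimated that ≥ 60 control subjects (MRE normal) will be required for the study". For the other group it says: "It is estimated that a sample of >60 cases (with abnormal MRE scans) would be needed". It then repeats the ratio, "Case and controls will be recruited in a ratio of 1:1", and forecasts at least 66 subjects in each group from about 445 reviewed scans and a prevalence of 15% to 16.7%.

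The documents give no uptake rate for the Assess phase, no allowance for axial MRI scans that are not completed, no minimum for controls that is independent of case enrolment, and no rule for replacing controls who decline.

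**The concern.** Section 8.1 treats the number of controls as a fixed requirement, but the recruitment rule makes it a by-product of case enrolment. If MRE-positive patients decline the second consent, the control group shrinks with them even though MRE-negative subjects are not scarce.

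This matters because sensitivity is in the study's aim, and every false negative must come from an MRE-negative subject who has the reference assessment. The size of the MRE-negative sample is therefore the main driver of how precisely sensitivity is estimated. With few controls there may be only a handful of false negatives, or none, in which case sensitivity would read 100%.

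**Working it through.** **1. The plan's own forecast.** Inputs from section 8.1: 445 scans, prevalence 15%.

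445 x 0.15 = 66.75, stated as 66. The forecast reproduces with no further factor, so it assumes that every MRE-positive subject consents a second time and completes the axial MRI.

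MRE-negative subjects: 445 x 0.85 = 378.

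**2. Where the minimum is breached.** Under the rule, controls = 66 x case uptake. Keeping 60 needs 60/66 = 90.9% uptake. Six lost cases leave 60 controls; the seventh leaves 59.

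| Case uptake (assumed) | Controls under the rule |
|---|---|
| 95% | 62.7 |
| 91% | 60.1 |
| 90% | 59.4 |
| 80% | 52.8 |
| 70% | 46.2 |
| 50% | 33.0 |

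The threshold depends on which of section 8.1's inputs are used. Its 990 subjects at 50% consent give 495 scans, not the stated 445.

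| Scans | Prevalence | Expected cases | Uptake needed for 60 controls |
|---|---|---|---|
| 445 | 15% | 66 (stated) | 90.9% |
| 445 | 16.7% | 74.3 | 80.7% |
| 495 | 15% | 74.25 | 80.8% |
| 495 | 16.7% | 82.7 | 72.6% |

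If controls also decline at the same rate and are not replaced, 95% uptake already gives 66 x 0.95 x 0.95 = 59.6.

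**3. Supply.** 60/378 = 15.9% of the MRE-negative subjects would be enough, and 66/378 = 17.5% would supply the forecast number.

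**4. Effect on precision (illustration).** Assumptions that are not in the documents: PPV 70%, case uptake of 70% or 50%, estimates weighted back to the screened cohort (67 positive, 378 negative), and the false-negative rate of the whole MRE-negative pool applied to the age- and sex-matched controls. True sensitivity is set at section 8.1's 60%.

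- True positives in the cohort: 67 x 0.70 = 46.9.
- False negatives: 46.9 x 0.4/0.6 = 31.3, a rate of 31.3/378 = 8.3% among MRE-negatives.
- Estimate: TP/(TP + FN), with TP = 67 x (positives among cases)/(number of cases) and FN = 378 x (positives among controls)/(number of controls). Both counts are binomial.
- Chance of no false negative: (1 - 0.0827)^(number of controls).

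| Cases / controls | Expected false negatives | 95% range of estimated sensitivity | Chance of no false negative |
|---|---|---|---|
| 47 / 47 (70% uptake, current rule) | 3.9 | 0.41 to 0.87 | 1.7% |
| 47 / 66 | 5.5 | 0.44 to 0.83 | 0.3% |
| 34 / 34 (50% uptake, current rule) | 2.8 | 0.39 to 1.00 | 5.3% |
| 34 / 66 | 5.5 | 0.43 to 0.83 | 0.3% |

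With 34 cases, the standard deviation of the estimate is 0.149 with 34 controls and 0.106 with 66. With 67 cases and 66 controls it is 0.104, so losing cases alone costs sensitivity almost nothing; losing controls with them does. At PPV 50%, the chance of no false negative with 34 and 66 controls is 12.6% and 1.8%.

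**5. Why weighting must come with the change.** In an unweighted two-by-two table the expected counts give 23.8/(23.8 + 2.8) = 0.89 at 34/34 and 23.8/(23.8 + 5.5) = 0.81 at 34/66, both for a true sensitivity of 0.60. The unweighted figure is wrong under either design and moves with the case:control ratio.

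**The case against.** Much can be said for the plan. Section 8.1 forecasts 66 against a minimum of 60, so there is a margin of six. It states its consent and diagnosis inputs as lower bounds and calls the forecast conservative. Uptake among MRE-positive patients without known SpA may well be high: they have consented once, are telephoned and referred to the SpA clinic as routine care, and are asked for consent at that visit. The protocol also expects patients with axial pain to be over-represented among volunteers. The precision loss is modest unless the shortfall is severe, and sensitivity is imprecise even with 66 in each group (about 0.44 to 0.82 under the same assumptions).

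All of this stands, and it limits the point in three ways that a reader might overlook.

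- One might infer that any case shortfall breaches the minimum. It does not: the first six losses are absorbed, and more under section 8.1's other inputs.
- One might take 0.39 to 1.00 as the expected result. It belongs to 50% uptake, a stress case; the only 50% in the documents refers to the first, postal consent.
- One might read the 66 controls as already paid for. Section 8.1 gives a recruitment forecast, and section 12 gives one total sum with no scan count.

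The objection does not supply a safeguard. Nothing in the documents protects the control minimum if second-stage uptake is lower than hoped, and the protocol itself says that subjects may decline the scan and names claustrophobia as a difficulty.

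**Conclusion.** The point holds as a conditional weakness of the recruitment rule. On the stated forecast, case uptake below about 91% takes the control group under section 8.1's own minimum; on its other inputs the threshold lies between 73% and 81%. The shortage would be produced by the rule, since about 378 MRE-negative subjects are available.

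The cost to sensitivity is modest at 70% uptake and serious at 50%. Those sizes rest on the assumed uptake and PPV, on the pool-wide false-negative rate, and on a weighted analysis that section 8.2 does not contain.

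Two limits remain. The same shortfall also breaches the separate requirement of more than 60 cases, which a change to the control rule cannot cure. And the figure of 60 cannot be verified, because section 8.1 gives no null value, comparator or precision target. It is used here only as the plan's stated requirement.

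**What to change.** - **Sections 4.1, 4.3.2, 5.2.1.2, 5.2.2.2 and 8.1 (and the summary in 1.5):** state a control target that does not depend on case enrolment, namely the 66 already forecast and never fewer than 60 with a completed axial MRI. Draw controls at random from the MRE-negative list within age and sex strata taken from all MRE-positive subjects, not only those who enrol. Replace those who decline until the target is met.
- **Section 8.2:** estimate sensitivity and specificity with weights equal to the inverse of the sampling fraction, by MRE result and age/sex stratum, so that the estimates do not depend on the case:control ratio.

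Cost: protocol wording, a short addition to the analysis, and possibly more invitation letters. No scans are needed beyond the 66 controls that section 8.1 forecasts. Strict 1:1 pairing is lost if cases fall short, but section 8.2 plans no paired analysis. A shortfall in cases needs its own remedy, starting with an explicit allowance in section 8.1 for second-stage uptake and MRI completion.
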